### **Removal of Subjects from Therapy or Assessment**

Each subject will be informed of their right to withdraw from the study at any time and for any reason. Subjects may be withdrawn from treatment or assessment:

- If continuing in the study does not appear to be in the best medical interest of the subject, his/her participation may be terminated by either the Principal Investigator or the study director. Removal of an individual by the Principal Investigator will be reported to the Institutional Review Board and the appropriate regulatory agencies according to the guidelines of these groups.
- Subjects considered as treatment failure i.e. those who meet Lille criteria for failure will be removed from the study and will be offered alternative standard therapy by their treating physician.

Reasons for permanent discontinuation include the following:

- The subject decides to withdraw from the study.
- The Investigator may withdraw a subject from the study at any time if he considers that remaining in the study compromises the subject's health or the subject is not sufficiently cooperative.
- The study DSMB on behalf of NIH and the TREAT consortium may ask that a subject be withdrawn from the study if it considers that remaining in the study compromises the subject's health and after discussing the issue with the Principal Investigator.

The reasons for any subject withdrawal will be recorded on the study completion form of the case report form (CRF). The Investigator will inform the Sponsor in writing of the subject's early withdrawal for any reason.

Upon withdrawal from the study, any time after dosing has taken place, the subject will have a further hematology, serum biochemistry, urinalysis, and medical examination. Laboratory tests will be those outlined for the follow-up safety tests in Appendix 1.

If withdrawal is caused by an adverse event that the Investigator considers may be related to the Imm 124-E, it will be reported to the IRB and to the Sponsor.

Any serious unexpected adverse event which is thought to be possibly or probably related to the study drug must be reported to Sponsors by telephone within 24 hours of being informed of the SAE or on the next business day after a holiday or weekend, and then, a Serious Adverse Event form must be completed and faxed to the sponsors within 48 hours. The event must be reported to the IRB within 5 days.

In the event of any abnormalities considered to be clinically significant by the investigating physician, subjects will be followed up with appropriate medical management until the outcome is determined or stabilized, according to the Principal Investigator's clinical judgment. All follow-up information will be recorded in the subject's CRF until full subject recovery is achieved and the PI has stated that the subject is dismissed from the medical care. Subsequent follow-up will be documented in the subject's personal file.

The TREAT steering committee reserves the right to discontinue the study at any time for any reason. If applicable, the Investigator must implement NIAAA request to terminate the study in a time frame that is compatible with the subjects' well-being.

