**DISCONTINUATION FROM TREATMENT OF INDIVIDUAL SUBJECT:**

Reasons for interruption/discontinuation include the following:

- Grade 3 or 4 toxicity considered related to study medication (laboratory abnormalities must be confirmed within 3 days)
- The investigator may withdraw a subject from the study at any time if he/she considers that remaining in the study compromises the subject's health or the subject is not sufficiently cooperative.
- The study DSMB may ask that a subject be withdrawn from the study if it considers that remaining in the study compromises the subject's health and after discussing the issue with the Principal Investigator.

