## INVESTIGATIONAL PLAN

### Overall Study Design and Plan – Description

**Figure 1: Study Schema**

Subjects with severe AH (MELD score  $\geq 20$  and  $\leq 28$ ) about to receive prednisolone (40 mg/day x 28 days) will be randomized to receive either:

- Group A: 2400 mg/day Imm 124-E as 1200mg bid PO
- Group B: 4800 mg/day Imm 124-E as 2400mg bid PO
- Group C: Identical appearing placebo bid PO

Treatment will be for 28 days (**Fig. 1, above**). Given variable outcomes and response to corticosteroid therapy in patients with severe AH, a Lille model was developed by French investigators to identify subjects early in the course of treatment that are unlikely to benefit from continued treatment and in fact might have worse outcome. The Lille model takes into account patient's age, and at the start of therapy total bilirubin, albumin, creatinine, prothrombin time values and total bilirubin level on day 7 of therapy. It projects a 6-month survival probability of patients with a Lille score above 0.45 to be about 25% contrary to patients with a Lille score below this cutoff (85%). Subjects who meet the Lille criteria for failure of treatment on Day 7 or side effects requiring discontinuation of steroids will be removed from the study. Standard of care nutrition support and alcohol cessation recommendations will be provided to all subjects. Alcohol withdrawal will be managed per standard of care.

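### Day-7 Lille failures are removed from the study with no stated follow-up, in conflict with the ITT analyses after Day 7 and with 24-week adverse-event collection

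*Combined protocol and SAP*

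**What the plan says.** **The removal rule.** It appears twice in the combined protocol and SAP. *Removal of Subjects from Therapy or Assessment* states that "those who meet Lille criteria for failure will be removed from the study". *Overall Study Design and Plan – Description* repeats this for Day 7 and extends it: subjects with "side effects requiring discontinuation of steroids will be removed from the study".

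**What follows removal.**
- After withdrawal, "the subject will have a further hematology, serum biochemistry, urinalysis, and medical examination" (*Removal of Subjects*).
- There is one early discontinuation visit (*Unscheduled Visits*).
- Clinically significant abnormalities, adverse events (AEs) and serious adverse events (SAEs) already known are followed until resolved or stable (*Removal of Subjects* and the AE and SAE reporting sections).

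**What the analyses expect.**
- *Analysis Population* plans intent-to-treat (ITT) analyses of mortality at Days 30, 90 and 180, of MELD, discriminant function (DF) and liver function at Days 7 and 30, and of the mechanistic endpoints.
- *Adverse Events* collects events until 24 weeks after the first dose.
- *Subject Populations* puts every dosed subject in the safety analysis.
- *Subject Disposition* rules out replacing missing values.

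**The concern.** An ITT analysis of Day-180 mortality needs the Day-180 status of everyone randomised. No readable passage says how that status is obtained for a subject removed at Day 7.

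The loss would not be random. Removal depends on the Day-7 response, which is measured after randomisation and which the drug may change. It is also strongly prognostic by the protocol's own account. The design section cites a projected six-month "survival probability of patients with a Lille score above 0.45 to be about 25" per cent, against 85% below the cutoff. Analyses after Day 7 would then compare arms among early responders only.

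The primary endpoint is the safety profile. Removed subjects stay in the safety set, but new events and deaths after their exit may go unrecorded. Such data may not be recoverable once the trial is over, and the plan allows no imputation.

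**Working it through.** The plan gives no Lille failure rate and no expected number of deaths, so it has no figure of its own to reproduce. All results below apply only if removal is taken literally.

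**Inputs**
- 66 subjects in three arms of 22 (synopsis; *Determination of Sample Size*).
- Six-month survival of 25% for Lille failures and 85% otherwise (*Overall Study Design and Plan*), hence mortality of 75% and 15%. This is the model's general projection and may differ in a MELD 20–28 population.
- Failure rate f: not in the documents; 10%, 20% and 40% assumed. Subjects removed for steroid side effects are not counted.

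**Step 1: mortality**

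Mortality in all randomised = 0.75f + 0.15(1 − f). Share of deaths in the removed group = 0.75f ÷ that total.

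| f | Removed of 66 | Day-180 mortality, all randomised | Mortality, retained only | Deaths, all | Deaths among removed | Share of deaths |
|---|---|---|---|---|---|---|
| 10% | 6.6 | 0.075 + 0.135 = 21% | 15% | 13.9 | 5.0 | 36% |
| 20% | 13.2 | 0.150 + 0.120 = 27% | 15% | 17.8 | 9.9 | 56% |
| 40% | 26.4 | 0.300 + 0.090 = 39% | 15% | 25.7 | 19.8 | 77% |

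**Step 2: how this can hide an effect (illustration only)**

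Suppose the drug acted solely through Lille status and cut failure from 40% to 25%, both values assumed. Mortality would be 0.75 × 0.40 + 0.15 × 0.60 = 39% on placebo and 0.75 × 0.25 + 0.15 × 0.75 = 30% on drug. Among retained subjects it would be 15% in both arms.

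**Step 3: AE observation time lost**

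Assume constant hazards fitted to the survival figures: −ln(0.25)/180 = 0.00770 per day for failures and −ln(0.85)/180 = 0.000903 per day for the rest. Expected days alive within the 168-day AE window are (1 − e^(−168λ))/λ, which gives 94.2 per failure (87.4 of them after Day 7) and 155.9 per non-failure.

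Share lost = 87.4f ÷ [94.2f + 155.9(1 − f)]:
- f = 10%: 8.74 ÷ 149.7 = 5.8%
- f = 20%: 17.5 ÷ 143.6 = 12.2%
- f = 40%: 35.0 ÷ 131.2 = 26.6%

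A Lille score requires survival to Day 7. Running the hazards from Day 7 to Day 180 instead gives 6.0%, 12.5% and 27.2%.

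**Step 4: which analyses are touched**

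| Analysis | If removal is literal |
|---|---|
| Lille proportion; Day-7 endotoxin, MELD/DF and liver function | Unaffected |
| Mortality at Days 30, 90 and 180 | No status required for removed subjects |
| MELD/DF and liver function at Day 30 | No visit stated for removed subjects |
| Later endotoxin sample (Day 28 in *Secondary Endpoints*, Day 30 in Table 2) | Not taken in removed subjects |
| AEs to 24 weeks | Observation cut short, except for follow-up of known events |
| Membership of the safety set | Unaffected |

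**The case against.** **Removal may mean off treatment only.** The lead-in reads "Subjects may be withdrawn from treatment or assessment". Lille failure is missing from the list headed "Reasons for permanent discontinuation include the following" and from the synopsis list headed "Reasons for interruption/discontinuation include the following". *Study Procedures and Flow Chart* gives the schedule for each subject, and neither the AE window nor the ITT list makes an exception for removed subjects. That reading would make the documents consistent. It stands as a possible intention and limits the point to a conflict to reconcile. But no readable text says that removed subjects stay in follow-up, and both statements of the rule say the study, not the drug. The Figure 1 schema could not be read in the available text and might bear on this.

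**Existing follow-up would catch some events.** Abnormalities are followed until the investigator dismisses the subject from care, and SAEs and deaths must be reported. This stands in part. These routes depend on a problem already known, or on the investigator learning of a new one; none is a scheduled contact at Day 30, 90 or 180. Counts of related AEs suffer less, because causality is assessed only to 7 days after discontinuation.

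**The stakes are modest.** Mortality, MELD/DF and liver function are exploratory in a pilot, and no formal hypothesis test is planned for the primary safety comparison. That is correct. A biased descriptive mortality table is still misleading, and safety is the primary endpoint.

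**Stronger readings to avoid.**
- A reader might infer that removal contradicts the all-dosed safety set. It does not; it shortens observation.
- A reader might infer that the endotoxin analysis as a whole is undermined. It is not: endotoxin is also measured at Day 7, and *Subject Populations* admits subjects with at least 7 days of treatment.
- A reader might infer a case from power. None is made, because values from retained subjects who are off treatment may dilute the late effect.

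**Conclusion.** The conflict is real and should be resolved. Read literally, the removal rule leaves the ITT mortality analyses, the Day-30 MELD/DF and liver-function analyses and the 24-week AE collection without a stated source of data for Lille failures. The missingness would be strongly informative for mortality: even at the lowest assumed failure rate, over a third of projected Day-180 deaths fall in the removed group.

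The sizes rest on an assumed failure rate, on the cited survival figures holding in this population and, for AE time, on constant hazards. A reader might infer that data are certain to be lost. The documents do not establish that; they leave an ambiguity that sites could resolve differently.

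**What to change.** Leave the treatment decision as the protocol has it, and separate the end of treatment from the end of follow-up.

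1. In *Overall Study Design and Plan* and in *Removal of Subjects*, add: *Removal does not end follow-up. Unless consent is withdrawn, these subjects keep the Table 2 laboratory and AE assessments at Days 30, 90 and 180, and vital status is recorded to Day 180.*
2. Add a vital-status row to Table 2.
3. In *Analysis Population*, add: *All randomised subjects are counted in the mortality analyses.*
4. If the later endotoxin sample is also kept, flag values taken after removal and show results with and without them.

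If the sponsor does not intend this follow-up, *Adverse Events* and *Analysis Population* should say that collection and analyses after Day 7 cover retained subjects only and are not ITT.

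**Cost.** A few sentences and one table row; the laboratory and AE visits already exist in Table 2. The downsides are retention effort in sick patients, a small amount of extra analysis, and possible dilution of the late endotoxin effect.

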## **STUDY PRODUCT**

### **Study Medication Supply**

Imm 124-E will be provided to each site by Immuron. The medications will be stocked and dispensed from the investigational drugs pharmacy at each site.

### **Description of Study Product**

Name:	Imm 124-E
Characteristics & Physical State:	Off white powder equivalent to 1200mg of Imm 124-E hyperimmune bovine colostrum
Formulated & Supplied by:	Immuron Ltd
Storage Conditions:	Store in cool and dry place. Temperature controlled between 2°C and 8°C
Shipments:	Temperature controlled between 2°C and 8°C

Package: Plastic Aluminium Foil Poly Laminate Pouches

### **Description of Comparator Product**

Name: Placebo

Characteristics & Physical State: Off white high protein milk powder, ProMilk85®

Supplied by: Immuron Ltd.

Storage Conditions: Store in cool and dry place. Temperature controlled between 2°C and 8°C

Shipments: Temperature controlled between 2°C and 8°C

Package: Plastic Aluminium Foil Poly Laminate Pouches

### **Packaging and Labeling**

All clinical supplies will be packed and labeled in compliance with the Good Manufacturing Practices of drugs used in clinical trials. All study medications provided will be appropriately documented.

Imm 124-E will be supplied in Plastic Aluminium Foil Poly Laminate Pouches (sachets). The sachets will be labeled as following:

1. Investigational pharmacy at each recruiting center will label each sachet with the subject's study ID, subject's name, IMM-124E/placebo, batch number, and expiry date before dispensation. It will also state that the medication is only for the intended subject and is not to be shared.
2. Labels of the outer packaging (the package in which the sachet will be placed) will bear the details of the name of Immuron Ltd., the address and telephone number of the main contact for information on the product, route of administration, batch number of Drug Product and Placebo, a trial reference code (i.e., TREAT), the Study ID, Investigator name, directions for use, and the phrase "For Clinical Trial Use Only". Expiration date will be given in month/year format, and label will include storage conditions.

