**Key exclusion criteria:**

- Cow milk allergy, severe lactose intolerance and/or known or suspected allergy to any of the ingredients in IMM 124-E
- Other or concomitant cause of liver disease (Viral hepatitis, autoimmune liver disease, metabolic liver disease, vascular liver disease).
- Subjects who are known to be HIV positive.
- Active infection or sepsis (pneumonia by X-ray, positive blood or urine culture) Untreated spontaneous bacterial peritonitis based on > 250 polymorphonuclear (PMN) cells or positive culture. All subjects with enough ascites to be deemed safe for paracentesis, will undergo this procedure (as standard of care) to exclude spontaneous bacterial peritonitis.
- Acute kidney injury with serum creatinine > 1.5 mg/dl at time of randomization
- Evidence of acute pancreatitis (by imaging and lipase > 5 x ULN)
- Subjects who are pregnant or lactating
- Significant systemic or major illness that, in the opinion of the Investigator, would preclude the patient from participating in and completing the study.

- Subjects who are non-cooperative or unwilling to sign consent form.
- Active Gastrointestinal bleeding (e. g. hematemesis, melena)

(See body of protocol for full list of exclusions)

**TEST PRODUCT(S), DOSE AND MODE OF ADMINISTRATION:** The placebo and IMM-124E will both be presented as 1200mg of powder for reconstitution in Plastic Aluminium Foil Poly Laminate Pouches (sachets). The appearance of the active and placebo will be indistinguishable. Each subject will take two sachets each morning and then again in the evening. Consequently, each arm of the study will take the same number of doses per day. Subjects in:

- Group A (IMM-124E 2400mg/day) will receive one sachet of active and one sachet of placebo in the morning and again in the evening.
- Group B (IMM-124-E 4800 mg/day) will receive two sachets of active in the morning and again in the evening.
- Group C (Placebo - High protein milk powder) will receive two sachets of placebo in the morning and again in the evening.

**DURATION OF TREATMENT:** 28 Days

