### **Randomization Procedures**

This is a double blind study and therefore the study staff and the subjects will remain blinded to the code assignments throughout the study. Prior to administration, each participant will be assigned with an individual number and will be provided with IP packs according to the predetermined computer generated randomization list.

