### **Dispensing, Compliance and Accountability**

Eligible subjects will be randomly assigned to each of the study groups. Subject will be instructed to take the contents of two sachets of powder reconstituted with water twice daily. Subject ID pack dispensing will be documented in the Case Report Forms and on the Investigational Drug Administration Records.

To prepare the study drug immediately before administration, add the powder to a cup and add approximately four tablespoons of water to the cup, stir gently for 1 minute until dissolved. Each subject will be required to drink the contents of both sachets in the morning before breakfast. Additional water may be added to the powder to ensure all the powder is taken. Subjects will be required not to eat for 2 hours after taking the drug. If a subject forgets to take the drug in the morning, he/she can take the drug during the day. He/she will be required not to ingest food for

2 hours before and 2 hours after taking the drug. The subject will also be instructed to take the contents of two sachets in the evening, at least 2 hours after eating.

The Investigator/designee is responsible for maintaining accountability for the receipt, dispensing, and return of all study medication.

The Investigational Pharmacy will be responsible for recording the receipt of all drug supplies and for ensuring the supervision of the storage and allocation of these supplies. When a shipment is received, the pharmacist verifies the quantities received and the accompanying documentation (e.g. certificate of analysis, date of manufacturing/expiry, storage instructions etc.) and return the acknowledgment of receipt to the Sponsor.

The Investigator/designee is responsible for keeping records of receipt of study medications, where the study medication is stored after arrival to the clinic and for maintaining detailed records, indicating dates and amounts of drug dispensed to whom ("subject by subject accounting").

Subjects will be requested to return all the used and unused sachets. That shall be recorded by the Investigator/designee in the CRF. The records should:

- distinguish between unopened (not dispensed) and unused (by study subjects) supplies;
- explain broken or lost drug supply; and
- account for all supplies and stock that may have been used.

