## **Confidentiality of Subject Data**

The Investigator will ensure that the confidentiality of the subjects' data will be preserved. In the CRF or any other documents submitted to the sponsor, the subjects will not be identified by their names, but by an identification system, which consists of their subject ID in the study. The Investigator will maintain documents not meant for submission to the sponsor, e.g., the confidential subject identification code and the signed informed consent forms, in strict confidence.

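### The sachet label must carry a batch number and expiry date with no provision for masking them; if these differ between active and placebo, a Group A dose can be recognised from its two sachets.

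*Combined protocol and SAP*

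**What the plan says.** Item 1 of Packaging and Labeling has the investigational pharmacy "label each sachet with the subject's study ID, subject's name, IMM-124E/placebo, batch number, and expiry date before dispensation". Batch number and expiry date are both in the singular and apply to each sachet. Item 2 covers the outer package, which is to show the "batch number of Drug Product and Placebo" among other details.

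The two products are described separately. The active is "Off white powder equivalent to 1200mg of Imm 124-E hyperimmune bovine colostrum"; the placebo, under Description of Comparator Product, is a high-protein milk powder.

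The Synopsis (test product and dose) gives the content of each dose. Group A "will receive one sachet of active and one sachet of placebo in the morning and again in the evening". Group B takes two active sachets per dose and Group C two placebo sachets.

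On handling, Dispensing, Compliance and Accountability says: "Subjects will be requested to return all the used and unused sachets". The investigator or a designee enters the returns in the CRF. Randomization Procedures promises that "the study staff and the subjects will remain blinded to the code assignments throughout the study".

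**The concern.** Powders that look alike protect the blind only if nothing printed on the container separates them. A batch number normally identifies one manufactured product, and these two powders are different materials. The design makes the label unusually informative because the low-dose arm mixes both products within each dose. A subject or staff member need not know what any number means to notice that the two sachets of a dose do not match.

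What is at stake is the primary endpoint. Under Primary Endpoint it is the safety profile, and under Subject Disposition it is reported as incidence and severity of adverse events. Events are elicited by questioning subjects, and the investigator grades severity and judges causality. Knowledge of the arm could affect what subjects report, how severe it is called and whether it is attributed to the drug.

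**Working it through.** **The plan's own supply count.** From the Synopsis, 2 sachets × 2 doses per day × 28 days = 112 sachets. At two sachets per box, 112 / 2 = 56 packs. Both figures agree with Method of Assigning Subjects to Treatment Groups, so there is one pack per dose.

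**Sachets dispensed per subject over 28 days**
- Group A: 1 × 2 × 28 = 56 active and 56 placebo
- Group B: 2 × 2 × 28 = 112 active
- Group C: 2 × 2 × 28 = 112 placebo

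**What a pack would show.** Assume that each sachet carries its own product's batch number and date, that these differ between products, and that one batch per product is in use at a time.
- Group A: two different numbers in each of the 56 packs
- Group B: two matching numbers, the active batch
- Group C: two matching numbers, the placebo batch

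**Share of arms guessed correctly, 22 subjects per arm, 66 in total**
- Labels the same for both products: 22 / 66 = 33%
- Pair pattern visible, batch content unknown, so Group A is recognised and B versus C is a coin toss: (22 + 0.5 × 44) / 66 = 44 / 66 = 67%
- Batch content also known: 66 / 66 = 100%

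The range is therefore 33% to 100%, depending on how labels are printed and what the reader knows. With several batches of one product in circulation, a Group B or C pack might also mismatch, and the pair pattern would be less informative than 67% suggests.

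**Do the stated safeguards cover this?** Method of Assigning Subjects lists identical appearance and packaging, coded boxes, a sealed master list and dispensing by the pharmacist alone. The first concerns the powder and its pack. The next two protect the link from code to arm. The last keeps the pharmacist apart from other study work. None of them masks a number printed on a sachet that leaves the pharmacy and later comes back.

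**The case against.** The strongest reply is that the documents never say the batch number is product-specific, or that numbers or dates differ between active and placebo. The product wording in item 1 is most naturally fixed dual text, and the batch entry beside it could follow the same convention. Pharmacists work from coded boxes and a sealed list, which fits poorly with printing a product-specific number on each sachet. Dispensing also follows a sponsor-supplied written procedure whose stated purpose is to keep the blind; masking may be set out there, and it is not among the documents. All of this stands, and it is why the point is a risk. It does not remove the risk, because the only labelling rule that is written down asks for the number and the date and is silent on masking.

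A reader might also infer more than the text supports:
- *The outer label reveals the arm.* Read literally, item 2 lists both batches on every package, so it shows no arm. It would matter only if it also marked which number belongs to which product and so became a key to the sachets.
- *Groups B and C are separated by the label alone.* They are not. Someone must first learn what one batch contains, and no section gives that knowledge to those who rate events.
- *The person who logs returns is the person who rates events.* The returns section allows a designee, and nothing says that both tasks fall to one person.
- *The subject's name on the sachet breaches Confidentiality of Subject Data.* The statement there that "the subjects will not be identified by their names, but by an identification system" is limited to the CRF and documents sent to the sponsor. Sachets are neither.

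Finally, the adverse-event comparison is described under Subject Disposition as carrying no formal hypothesis test, and the endotoxin comparison, on which the sample size rests, is a laboratory assay. That limits the consequences for inference. It does not protect the descriptive safety profile, which is the stated primary endpoint.

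**Conclusion.** The concern holds as an unaddressed risk to the blind. If batch numbers or expiry dates differ between the two products and each sachet shows its own, Group A (22 of 66 subjects) can be recognised from a single pack. Correct guessing of the arm would rise from 33% to about 67%, and to 100% once a batch is matched to its product. These figures measure how readable the label would be to someone who knows the design. They do not estimate how many people would be unblinded or how large any bias would be. Nor is 112 sachets a measure of actual use, since subjects who meet the Lille failure criteria at day 7 leave the study.

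A reader might conclude that the blind is broken by design. The documents do not support that, because whether the numbers and dates differ is not stated. If supplies already carry a masked number and a common date, the matter reduces to a missing sentence in the protocol.

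**What to change.** Amend items 1 and 2 of Packaging and Labeling so that sachet and outer labels are identical across arms and products. Each label should carry:
- the fixed text *IMM-124E or placebo*, stated to be the same on every label;
- the study ID;
- a blinded pack code or, alternatively, both batch numbers on every sachet without marking which is which;
- one common expiry date, the earlier of the two products' dates.

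Keep the link from pack to batch only with the data coordinating center and unblinded supply or pharmacy staff. If masking is already in the sponsor's dispensing procedure, say so in this section and refer to it.

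The cost is new label wording, a line in the pharmacy instructions and a slightly shorter labelled shelf life. With a pack code, a sachet can no longer be traced to its batch directly, so any batch query or recall has to go through the code list.
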